Appendix A

Dianeal Solution

Dianeal PD-2 Peritoneal Dialysis Solutions are sterile, nonpyrogenic and contain no bacteriostatic or antimicrobial agents or added buffers.

Each 1000 mL of Dianeal Peritoneal Dialysis Solution contains:

Components	Contents
Glucose, BP	1.5 % - 15.0 g
Sodium Chloride, BP	5.38 g
Sodium Lactate	4.48 g
Magnesium Chloride Hexahydrate, BP	50.8 g
Calcium Chloride Dihydrate, BP	PD-2 257 mg
Water For Injections, BP	QS

Dianeal PD-2 Peritoneal Dialysis Solution with 1.5% Glucose:

Components	Contents
Glucose .H2O	76 mmol/L
Sodium	132 mmol/L
Calcium	1.75 mmol/L
Magnesium	0.25 mmol/L
Chloride	96 mmol/L
Lactate	40 mmol/L
Approximate Osm	346 mOs

Title: Direct Peritoneal Resuscitation in Gastroschisis

PI: [name]

Sponsor: UAMS

Appendix B

Gastroschisis

Initial Treatment

Place infant right side down

- Replogle to LIS
- Cover lower body with bowel bag
- Antibiotics: Ampicillin & Gentamicin

Admission labs

Silo Placement at Bedside

Preparation

- Ensure there are no perforations, ischemic bowel, atresias
- Make sure Replogle is in place and functional
- Lay patient on right side if bowel appears ischemic

Equipment

- Gather from the OR: Concept battery powered pencil cautery.
- Gather from NICU: Betadine, umbilical artery catheterization tray, and silos size 3-6 (box in NICU).

Technique Tips

- Splay mesentery to avoid kinking
- If opening fascia, inject lidocaine first
- Cauterize fascia on top of the back end of a forcep
- Open fascia upward first about 0.5 cm
- Try not to cut skin unless needed
- Measure defect & pick silo size resulting in 1 cm overlap
- Lubricate silo with sterile saline
- Caution during placement → Liver & Spleen
- Ensure contents move easily within silo and are viable
- Consider milking meconium distally out of colon, succus proximally into Replogle and emptying bladder with palpation.

Silo Reduction

- Carefully apply umbilical or trach tape to silo sequentially daily.
- Do not clamp bowel
- Once at level of fascia, patient is taken to operating room for closure.

Post-Closure

- When Replogle output clears and decreases, start formula or EBM and follow NICU protocols.
- Continue Zantac or Prevacid
- Glycerin enemas BID until stooling spontaneously

Failure to tolerate initiated diet 3-4 wks after closure → Contrast Enema to rule out atresia or meconium plugs.

Title: Direct Peritoneal Resuscitation in Gastroschisis

PI: [name]

Sponsor: UAMS

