NICU – Neonatal Intensive Care Unit

OB/GYN – Obstetrics & Gynecology

OG Tube – Orogastic Tube

PI – Principal Investigator

PTN – Pediatric Trials Network

RR – Respiratory rate

SAE – Serious Adverse Event

SoC – Standard of Care

SpO₂ – Pulse Oximetry

TPN – Total Parenteral Nutrition

UAMS – University of Arkansas for Medical Sciences

Title: Direct Peritoneal Resuscitation in Gastroschisis

PI: [name]

Sponsor: UAMS

Background and Rationale

Gastroschisis is a clinical condition characterized by a defect in the normal development of the abdominal wall. The defect is present to the right of the umbilicus leading to *in utero* bowel evisceration and exposure to amniotic fluid. After birth and prior to operation, the usual treatment consists of covering the bowel with an impermeable plastic bag to prevent additional fluid losses and bowel desiccation. Subsequent operative intervention occurs either in the operating room or in the neonatal intensive care unit. Two surgical options include primary closure of the abdomen or placement of a silastic silo followed by subsequent closure several days later as a staged procedure. The main reason the abdominal wall is not closed initially is due to fear of abdominal compartment syndrome, a condition caused by high intra-abdominal pressures leading to respiratory and circulatory compromise. The key points of the initial surgery involve examining the intestine for any signs of atresia, bowel compromise, and either placement of the bowels back into the abdomen or a spring-loaded silo.

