The investigational product will be kept in a secure, limited-access storage in the ACRI research pharmacy under the direction of the research pharmacists who will be responsible for maintaining the supply according to the manufacturer's specifications, dispensing the drug for administration, and maintaining all drug accountability logs.

Study Population

We will prospectively enroll all neonates with the diagnosis of gastroschisis presenting to ACH within 12 hours after birth for whom consent is signed by the parent(s)/LAR. We anticipate enrolling 40 subjects at Arkansas Children's Hospital. All subjects that have their abdominal wall defect closed will be defined as having completed active participation in the study.

Eligibility Criteria

Inclusion criteria:

- Diagnosis of Gastroschisis
- Male or Female, any ethnicity
- Neonates [18]

Exclusion criteria:

- Primary gastroschisis repair
- Vanishing gastroschisis
- Encapsulating peritoneal sclerosis
- Infants < 2 kg and < 34 weeks gestation
- Infants > 12 hours at enrollment
- Severe hypotension, defined as either:
 - Mean arterial blood pressure (MAP) < gestational age in weeks, or
 - Systolic blood pressure (BP) < 45 or diastolic BP < 20
- Severe Hypertension defined as Systolic BP > 90 or diastolic > 60
- Culture-positive sepsis
- Known or strongly suspected inborn errors of metabolism
- Significant cardiac disorders, including cyanotic congenital heart disease, ductal-dependent congenital heart disease, and critical congenital heart disease (lesions requiring surgery or catheter-based intervention in the first year of life)
- Respiratory failure, defined as any requirement of positive pressure ventilation at the time of enrollment, or FiO₂ > 50%

Title: Direct Peritoneal Resuscitation in Gastroschisis

PI: [name]

Sponsor: UAMS

- Any other condition, that, in the opinion of the investigator, might interfere with the safe conduct of the study or place the subject at increased risk
- Lactic acidosis with at least one or more of the following:
 - Characterized by increased blood lactate levels ($> 5 \text{ mmol/L}$) on two occasions at least 6 hours apart
 - Severe metabolic acidosis with an arterial pH ≤ 7.0
 - Bicarbonate < 14 or $\text{CO}_2 < 12$
 - Base excess of $> -10 \text{ mEq/L}$
- Neonatal Acute Renal Failure, defined as serum creatinine $> 2.0 \text{ mg/dL}$ with anuria in the first 12 hours of life
- Neonatal Acute Hepatic Failure, defined as INR ≥ 3 [19]

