- Liver function test abnormalities defined as AST > 200 , ALT > 200 , GGT > 100 [19]
- Electrolyte abnormalities, defined as:
 - Sodium < 130 or $> 150 \text{ mEq/L}$
 - Potassium < 3.0 or $> 6.5 \text{ mEq/L}$
- Hyperglycemia ($> 150 \text{ mg/dL}$) or hypoglycemia ($< 40 \text{ mg/dL}$)

Note: Potentially eligible subjects may be randomized and the silo placed according to the assigned study arm before all laboratory results are available. Laboratory values will be verified for eligibility prior to administration of DPR. Any ineligible subjects will be withdrawn from the study and may be replaced.

Randomization

The randomization schedule will be generated by the biostatistics department and the Principal Investigator (PI) will maintain a randomization log listing the subjects' ID and study arm assignment. Subjects will be randomized to either the DPR group or SoC group. If the subject is assigned to receive DPR, the ACRI Research Pharmacist will dispense the 1.5% Dianeal solution. The PI will calculate the dose to be distributed based on the subject's weight at the time of enrollment and administer the appropriate volume of 1.5% Dianeal solution as per instructions in the *Investigational Product* section.

Study Design and Procedures

This is a prospective double-arm study designed to evaluate the tolerability of direct peritoneal resuscitation (DPR) in neonates with gastroschisis. The experimental arm (DPR group) will receive adjuvant DPR with standard treatment for gastroschisis (staged silo closure). The control arm (SoC group) will receive standard treatment for gastroschisis only. All subjects will be placed in a silo shortly after birth and within 2 hours of admission to the NICU and subsequently serially reduced in silo with umbilical tape until the bowel contents are at the level of fascia and deemed suitable for closure.

A. SoC Group

[figure not shown]
The SoC group will be placed in silo within 2 hours of admission to the NICU per standard practice. These subjects will have no change in current clinical management by the neonatologists or pediatric surgeons and will not receive peritoneal dialysis fluid.

B. DPR Group

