 - a. Maternal race/ethnicity, age, prenatal care, prenatal vaccination history* (as available) [21], any congenital anomalies that were diagnosed prenatally, maternal substance use history, infant or maternal toxicology screen results, maternal infection history* (including risk factors for infections (as available)) [21], maternal antenatal conditions, antenatal steroids, antenatal magnesium, prenatal ultrasound findings, obstetric antenatal conditions, multiplicity of births, delivery type, APGAR score, indications for C-section
4. Infection
 - a. Blood stream infection, total ventilation days, surgical site infection, and ventilator-associated pneumonia, drain or catheter-related infections
5. Surgery
 - a. Respiratory mode support with surgical time frame, lab values with surgical time frame, complications associated with surgical time frame, surgical procedures, complications
6. Interventions during this admission as recorded by the NICU for the Children's Hospital Network Database
7. Date of discharge from NICU
 - a. Discharge disposition
8. Patients discharge to home/foster care
9. Mortality
10. GI
 - a. Did this infant have functional or structural short gut syndrome at the time of discharge?
 - b. Classification of gastrochisis at time of silo placement - Imaging to be taken at time of initial evaluation.
 - i. Simple
 - ii. Complex: atresia, stenosis, perforation, volvulus
 - iii. Appearance

Title: Direct Peritoneal Resuscitation in Gastroscisis

PI: [name]

Sponsor: UAMS

1. Pristine
2. Matted bowel with peel
3. Staining of amniotic fluid
4. Staining of bowel serosa
- c. # of days of empiric antibiotics
- d. Type/Staging of closure of gastroscisis
- e. Complications associated with closure
- f. Additional closure techniques(s)
- g. Closure timing

11. Other complications

- a. Bacterial overgrowth, late ischemia, NEC, stricture, volvulus, malabsorption, transfer for bowel or liver transplant

12. Feeding and medications

- a. Medications and immunizations [21]
- b. Hyperalimentation
- c. Enteral feedings
 - i. Route of feeding at initiation
 - ii. Reached 100 kcal/kg/d
 - iii. Route of feeding when reached 100 kcal/kg/d
 1. Type of gavage/gastrostomy tube feeding
 - iv. Type of enteral nutrition when reached 100 kcal/kg/d
 - v. Change in feeding regimen
 1. Date change was made
 2. Why change was made

13. Ultrasound

- a. Cumulative motility
- b. Mean motility

14. Additional data

- a. Gastrostomy tube residuals: date, time, and cc

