¹¹ The clinical course of each AE should be followed until resolution, stabilization, or until it has been determined that the study treatment is not the cause.

Title: Direct Peritoneal Resuscitation in Gastroschisis

PI: [name]

Sponsor: UAMS

Schedule of Procedures and Assessments

Screening (Day of Birth from 0-12 hours)

- Informed Consent
- Randomization
- Silo placement (within 2 hours of admission to the NICU)
 - JP drain placed and secured per randomization
- Vital signs: heart rate (HR), respiratory rate (RR), MAP/BP, pulse oximetry (SpO₂)
- Weight
- Routine Daily labs per NICU standard practice:
 - Complete CBC
 - Magnesium
 - Renal Function Panel (sodium, potassium, chloride, CO₂, BUN, creatinine, calcium, phosphate, albumin, glucose)
- Research lab (both groups):
 - Lactate
- G-tube placement per NICU standard practice

Staged Reduction Day 1 (Day of Birth from 0-24 hours)

- Verify laboratory values for eligibility
- Instill DPR for DPR group every 6 hrs (± 30 minutes)
- Blood glucose within 1 hour prior to infusion and 1 hour (± 15 minutes) post-infusion for the first 24 hrs of DPR
- Vital signs every 6 hrs (± 30 minutes): HR, RR, MAP/BP, SpO₂
- Weight
- Strict intake/output every 6 hrs (± 30 minutes)
- DPR Group research labs every 6 hrs (± 30 minutes):
 - Sodium
 - Potassium
 - Glucose
 - Lactate
- Adverse events

Day of Life 1 - Day of Life 7

- Instill DPR for DPR group every 6 hrs (± 30 minutes) until abdomen is closed
- Blood glucose within 1 hour prior to infusion and 1 hour (± 15 minutes) post-infusion for the first 24 hrs of DPR
- Vital signs every 6 hrs (± 30 minutes) for 48 hours after maximum dialysate infusion volume (100 mL) is reached, then every 12 hrs (± 30 minutes): HR, RR, MAP/BP, SpO₂
- Weight
- Strict intake/output every 6 hrs (± 30 minutes) for 48 hours after maximum dialysate infusion volume (100 mL) is reached, then every 12 hrs (± 30 minutes)
- Routine daily labs per NICU standard practice:
 - Complete CBC
 - Magnesium
 - Renal Function Panel (sodium, potassium, chloride, CO₂, BUN, creatinine, calcium, phosphate, albumin, glucose)

Title: Direct Peritoneal Resuscitation in Gastroschisis

PI: [name]

Sponsor: UAMS

- SoC Group research lab (every 24 hrs (\pm 30 minutes) at the same time as routine daily labs:
 - Lactate
- DPR Group research labs every 6 hrs (\pm 30 minutes) for 24 hours after maximum dialysate infusion volume (100 mL) is reached, then every 12 hrs (\pm 30 minutes):
 - Sodium
 - Potassium

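### The plan does not fix the bowel examination, the silo-or-primary-repair decision or the simple/complex class before assignment, so removal after randomization can depend on arm

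*Combined protocol and SAP*

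**What the plan says.** **Order of events.** The Screening list in the Schedule of Procedures and Assessments runs consent, randomization, then silo placement, with "JP drain placed and secured per randomization". The Calendar keeps that order, and its first footnote makes silo alone or silo plus drain depend on the assigned group. The note closing the Eligibility Criteria also has the silo placed by arm. Neither the Calendar nor the Schedule has an entry for examining the bowel or confirming surgical eligibility.

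**What is learned at the procedure.** The Background says of gastroschisis surgery in general: "The key points of the initial surgery involve examining the intestine for any signs of atresia, bowel compromise", followed by "either placement of the bowels back into the abdomen or a spring-loaded silo". Data to be obtained, item 10 (GI), records the simple/complex class at silo placement, with imaging at initial evaluation. It defines the second class as "Complex: atresia, stenosis, perforation, volvulus".

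**Who takes part.** The Study Population section enrols all neonates with gastroschisis who meet the 12-hour limit and whose parents consent. "Primary gastroschisis repair" is an exclusion; complex gastroschisis is not. Study Design and Procedures states: "All subjects will be placed in a silo shortly after birth and within 2 hours of admission to the NICU". Appendix B, under Preparation for the silo, says "Ensure there are no perforations, ischemic bowel, atresias" and gives no action if one is found.

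**What happens to ineligible infants.** The eligibility note lets any ineligible randomized infant be withdrawn and replaced. Subject Withdrawal from Study ends data collection for withdrawn infants. Data Analysis defines no analysis population.

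**The concern.** Whoever places the silo must know the arm, because only DPR infants receive the drain and it goes in during the same procedure. No masking is described. If the bowel is examined, or the infant judged suitable for a silo, at that step, then an eligibility fact and a probably prognostic class are settled with the arm known.

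The exclusions include any condition that the investigator thinks might place the infant at increased risk. Only the DPR arm adds an intraperitoneal drain and dialysate, so for an infant with compromised bowel that judgement could differ by arm. Nothing requires it to be made before assignment.

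The stake is the primary comparison of mean time to full feeds. If slow infants leave one arm more often and are replaced, that arm looks better with no treatment effect. Because data collection stops at withdrawal, the loss cannot be repaired in analysis.

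**Working it through.** **Yardstick.** The plan gives no figure on this point. Its design figures are 20 per arm, a 6-day difference, SD 7, two-sided 5% and at least 80% power (Data Analysis). The noncentrality is 6 / (7 × √(2/20)) = 2.71. This gives 77.4% power by the normal approximation and 75.2% by the exact t-test with 38 degrees of freedom. That shortfall is a separate matter; only the 6-day target is used as a yardstick here. Losing 1, 2, 3 or 4 infants from one arm without replacement lowers exact power to 74.1%, 72.8%, 71.4% or 69.9%. Lost power is therefore a minor issue beside selective loss.

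**Assumptions.** The documents give neither the share of complex infants nor their delay. Assume:
- share complex f = 10% or 20%;
- extra days to full feeds D = 10, 20 or 30;
- a fraction g of complex infants removed from one arm only, and replaced by new enrolments so that the arm stays at 20.

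**Formula.** After removal and replacement, the complex share in the affected arm is f′ = f(1 − g) / (1 − fg). The spurious difference in means is (f − f′) × D.

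- Half removed, f = 10%: f′ = 0.05/0.95 = 0.0526. The difference is 0.0474 × 10 = 0.47 days, up to 0.0474 × 30 = 1.42 days.
- Half removed, f = 20%: f′ = 0.10/0.90 = 0.1111. The difference is 0.0889 × 10 = 0.89 days, up to 0.0889 × 30 = 2.67 days.
- All removed: f′ = 0. The difference runs from 0.10 × 10 = 1.0 day to 0.20 × 30 = 6.0 days.
- Same fraction removed in both arms: the difference is zero by symmetry.

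**Type I error.** This was simulated with no true effect, 40,000 trials per setting, normal outcomes with SD 7 around 10 days (the historical mean for simple gastroschisis), complex infants shifted by D, and the planned two-sided t-test.

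| f | D (days) | Half leave one arm: bias (days), type I error | All leave one arm: bias (days), type I error |
|---|---|---|---|
| 10% | 10 | 0.47, 5.4% | 1.0, 6.8% |
| 10% | 20 | 0.95, 6.1% | 2.0, 10.5% |
| 10% | 30 | 1.42, 6.5% | 3.0, 13.2% |
| 20% | 10 | 0.89, 6.5% | 2.0, 12.7% |
| 20% | 20 | 1.78, 8.4% | 4.0, 25.8% |
| 20% | 30 | 2.67, 9.3% | 6.0, 35.7% |

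With no removal the simulated error is 4.8-5.1%.

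**Per infant.** With 20 per arm, replacing one infant who is 20 days slower moves the arm mean by 20/20 = 1 day.

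**The passages side by side.** The enrolment statement, the all-subjects-get-a-silo statement and the complex class in the data list together imply that infants with atresia or perforation take part. Appendix B can be read as saying that an infant with either should not go on to a silo. No passage says what happens to such an infant after randomization.

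**The case against.** A reader might infer that the bowel is examined only after the surgeon knows the arm. The documents do not say so. Appendix B lists the check under Preparation, ahead of silo technique, and imaging is taken at initial evaluation, so some or all of the inspection could precede randomization. The order is unspecified.

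A reader might also infer that Appendix B excludes complex infants. It is a routine-care checklist with no eligibility or withdrawal rule. The same list goes on to cover positioning when the bowel appears ischemic, and it later foresees ruling out atresia in infants who fail feeds 3-4 weeks after closure. It can be read as a prompt to inspect. What stands is that it gives no consequence for a positive finding.

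Other limits are fair:
- The Background describes surgical options in general. At this site nearly all infants get a silo and primary closure is rare, so few would leave by that route, and those who did need not be slow feeders.
- The withdraw-and-replace note is written around laboratory results, although its wording covers any ineligible infant.
- The investigator-opinion exclusion applies to both arms, and no passage says it is reapplied to DPR infants after a bowel finding.
- The planned t-test does not use simple/complex, so misclassification alone would not change the primary result. Removal by arm would.

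None of this closes the gap: no passage places these decisions before assignment.

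**Conclusion.** The point holds as a gap in sequence and handling. Eligibility and class can be settled with the arm known, and the rules allow removal, replacement and loss of data afterwards. That makes arm-dependent removal possible; the documents do not show that it will happen, or in which direction. It would favour DPR only if slower infants left the DPR arm more often.

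On assumed shares of 10-20% and delays of 10-30 days, the bias is about 0.5-2.7 days with type I error of about 5-9% if half the complex infants leave one arm only. If all leave one arm and none the other, it is 1-6 days and about 7-36%. It is zero if removal does not differ by arm. A reader might take the upper figures as the expected bias; they are a worst case. The change is worth making because it is cheap and the loss could not be repaired later.

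**What to change.** 1. In the Calendar and in the Screening list of the Schedule, put these steps before the assignment is opened: examine the bowel, record silo or primary repair, record simple or complex, and confirm surgical eligibility. Then open the assignment and place the silo with or without the drain.
2. Reconcile the Eligibility Criteria, Study Design and Procedures, item 10 of the data list and Appendix B on whether infants with perforation, ischemic bowel or atresia take part, and state what follows a positive check. That is a clinical decision for the sponsor. Apply the answer identically in both arms.
3. State in Data Analysis that infants found complex after assignment stay in their randomized arm for the primary analysis. Align the eligibility note and the withdrawal section so that their outcome data continue to be collected unless consent is withdrawn.

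The cost is protocol wording and a change of order within one bedside procedure. The assignment has to be opened at the bedside inside the two-hour silo window, with a sterile drain at hand before the arm is known. The sample size does not change.

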Appendix C

NICU Feeding Protocols

Arkansas Children's Hospital
Recommended Neonatal Enteral Feeding Guidelines
Approximately >1500 grams and > 32 weeks

[figure not shown]

Patient Name: _____

Date of Birth: _____

Birth Weight: _____

Day of Feeds	Date	Weight	Composition	Volume
1	_____	_____	20 BM/20 PF	20 mL/kg/d
2	_____	_____	20 BM/20 PF	40 mL/kg/d
3	_____	_____	20 BM/20 PF	60 mL/kg/d
4	_____	_____	20 BM/20 PF	80 mL/kg/d
5	_____	_____	22 BM/22 PF	80 mL/kg/d
6	_____	_____	22 BM/22 PF	100 mL/kg/d
7	_____	_____	24 BM/24 PF	100 mL/kg/d
8	_____	_____	24 BM/24 PF	120 mL/kg/d
9	_____	_____	24 BM/24 PF	140 mL/kg/d
10	_____	_____	24 BM/24 PF	150 mL/kg/d

BM = Breast Milk

PF = Preterm Formula

B = Beneprotein

Goal is to begin trophic feeds by the first 2-7 days of life at the discretion of the neonatologist.

This form is not a permanent part of the medical record

Appendix D**Adverse Event Table – Laboratory Values [23]**

	Adverse Event		Serious Adverse Event	
	Conventional Units	International System (SI)	Conventional Units	International System (SI)
Electrolytes				
Hyponatremia	120–124 mEq/L	120–124 mmol/L	<120 mEq/L	<120 mmol/L
Hypernatremia	150–159 mEq/L	150–159 mmol/L	>159 mEq/L	>159 mmol/L
Hypokalemia	2.0–2.5 mEq/L	2.0–2.5 mmol/L	<2.0 mEq/L	<2.0 mmol/L
Hyperkalemia	7–7.9 mEq/L	7.0–7.9 mmol/L	>7.9 mEq/L	>7.9 mmol/L
Bicarbonate: Low	12–14 mEq/L	12–14 mmol/L	<12 mEq/L	<12 mmol/L
Bicarbonate: High	35–45 mEq/L	30–45 mmol/L	>45 mEq/L	>45 mmol/L
Hypocalcemia (ionized)	4.1–4.2 mg/dL	0.7–1.05 mmol/L	<4.1 mg/dL	<0.7 mmol/L
Hypercalcemia (ionized)	5.4–5.7 mg/dL	1.3–1.6 mmol/L	>5.7 mg/dL	>1.6 mmol/L
Renal				
BUN	60–100 mg/dL	21.42–35.7 mmol/L	>100 mg/dL	>35.7 mmol/L
Creatinine	1.5–2.5 mg/dL	132.6–221 µmol/L	>2.5 mg/dL	>221 µmol/L
Endocrine				
Hypoglycemia	25–36 mg/dL	1.4–2 mmol/L	<25 mg/dL	<1.4 mmol/L
Hyperglycemia	250–500 mg/dL	13.9–27.8 mmol/L	>500 mg/dL	>27.8 mmol/L
Gastrointestinal				
Aspartate aminotransferase	200–1000 U/L	3.34–16.7 µkat/L	>1000 U/L	>16.7 µkat/L
Alanine aminotransferase	200–1000 U/L	3.34–16.7 µkat/L	>1000 U/L	>16.7 µkat/L
Alkaline phosphatase	1000–1400 U/L	16.4–23.4 µkat/L	>1400 U/L	>23.4 µkat/L
Conjugated bilirubin	3–10 mg/dL	51.3–171 µmol/L	>10 mg/dL	>171 µmol/L
Gamma-glutamyl transferase	100–125 U/L	1.7–2.1 µkat/L	>125 U/L	>2.1 µkat/L
Hypertriglyceridemia	500–1200 mg/dL	5.7–13.6 mmol/L	>1200 mg/dL	>13.6 mmol/L
Hematologic				
Leukopenia	0.5–2 × 10 ³ /µL	0.5–2 × 10 ⁹ /L	<0.5 × 10 ³ /µL	<0.5 × 10 ⁹ /L
Leukocytosis	30–50 × 10 ³ /µL	30–50 × 10 ⁹ /L	>50 × 10 ³ /µL	>50 × 10 ⁹ /L
Anemia: hemoglobin	7–9 g/dL	70–90 g/L	<7 g/dL	<70 g/L
Anemia: hematocrit	20–26%	0.24–0.26	<20%	<0.24
Polycythemia: hemoglobin	23–24 g/dL	230–240 g/L	>24 g/dL	>240 g/L
Polycythemia: hematocrit	66–70%	0.66–0.7	>70%	>0.7
Thrombocytopenia	50–100 × 10 ³ /µL	50–100 × 10 ⁹ /L	<50 × 10 ³ /µL	<50 × 10 ⁹ /L
Thrombocytosis	450–1000 × 10 ³ /µL	450–1000 × 10 ⁹ /L	>1000 × 10 ³ /µL	>1000 × 10 ⁹ /L
Prothrombin time	18–22 seconds	18–22 seconds	>22 seconds	>22 seconds
Activated partial thromboplastin time	79–101 seconds	79–101 seconds	>101 seconds	>101 seconds
Lactate	45.1–90.1 mg/dL	5–10 mmol/L	>90.1 mg/dL	>10 mmol/L
Musculoskeletal				
Creatine kinase	470–600 U/L	7.9–10 µkat/L	>600 U/L	>10 µkat/L
Respiratory				
Acidosis: pH	7.10–7.19	7.15–7.19	<7.10	<7.15
Alkalosis: pH	7.50–7.60	7.50–7.60	>7.60	>7.60
pCO ₂ : low*	25–30 mEq/L	25–30 mmol/L	<25 mEq/L	<25 mmol/L
pCO ₂ : high*	55–65 mEq/L	55–65 mmol/L	>65 mEq/L	>65 mmol/L
Base Excess: low*	-10 – -15 mEq/L	-10 – -15 mmol/L	>-15 mEq/L	>-15 mmol/L
Base Excess: high*	+5 – +10 mEq/L	+5 – +10 mmol/L	>+10 mEq/L	>+10 mmol/L

*Laboratory values added to the original table

Adverse Event Table – Clinical Entities [23]

	Adverse Event	Serious Adverse Event
Gastrointestinal		
Necrotizing enterocolitis		Bell Stage II or III
Intestinal perforation		Intra-abdominal free air without preceding pneumatosis
Musculoskeletal		
Fracture	Fracture treated with immobilization	Fracture with any surgical intervention needed or known lasting sequelae
Respiratory		
Respiratory failure		Initiation of mechanical ventilation or some defined change
Pneumothorax	Present but no intervention required	Intervention required (e.g., chest tubes, sclerosis therapy and/or operative)
Apnea		Requiring initiation of mechanical ventilation
Pulmonary hypertension		Present and initiation of medical therapy to treat pulmonary hypertension (e.g., nitric oxide, milrinone, sildenafil)
Neurological		
Seizure		Present and treated with anticonvulsant
Intraventricular hemorrhage		Grade 3-4
Periventricular leukomalacia		Present on imaging
Cardiology		
Hypotension		Requiring pressors
ECG QTc prolongation	460 – 485 ms	> 485 ms
Supraventricular tachycardia	Episode resolves spontaneously or with vagal maneuvers	Requiring medical drug therapy or electroconversion to revert to sinus rhythm
Infectious Disease		
Wound infection	Requiring only local intervention (e.g., topical antimicrobial)	Requiring systemic antimicrobial therapy or surgery
Urinary tract infection		Positive urine culture treated with systemic antibiotics or antifungals
Cellulitis	Requiring only local intervention (e.g., antimicrobial)	Requiring systemic antimicrobial therapy or surgery
Bloodstream infection		Positive blood culture requiring systemic antimicrobial
Meningitis		Positive cerebral spinal fluid culture requiring systemic antimicrobial
Ophthalmologic		
Conjunctivitis	Requiring only local intervention (e.g., topical antimicrobial)	Requiring systemic antimicrobial therapy or surgery
Retinopathy of prematurity	Any stage	Any stage requiring surgical or medical intervention
Otolaryngology		
Hearing impairment		Confirmed hearing loss, either unilateral or bilateral
Drug mediated		
Infusion related reaction	Mild transient reaction or reaction that responds promptly to symptomatic treatment (e.g., antihistamines, NSAIDS, narcotics, IV fluids)	Prolonged reaction that does not respond promptly to symptomatic treatment (e.g., antihistamines, NSAIDS, narcotics, IV fluids) or life-threatening reaction that requires urgent intervention
Infusion site extravasation	Erythema with or without associated symptoms (e.g., edema, pain, induration, phlebitis)	Significant tissue injury leading to ulceration, necrosis, operative intervention indicated, or urgent intervention indicated
Injection site reaction	Tenderness with or without associated symptoms (e.g., warmth, erythema, itching, lipodystrophy, edema)	Significant tissue injury leading to ulceration, necrosis, operative intervention indicated, or urgent intervention indicated
Allergic reaction	Transient flushing, rash, drug fever that responds promptly to symptomatic treatment (e.g., antihistamines, NSAIDS, narcotics)	Prolonged reaction that does not respond promptly to symptomatic treatment (e.g., antihistamines, NSAIDS, narcotics, IV fluids) or life-threatening reaction that requires urgent intervention
Anaphylaxis	Acute onset of illness with skin and/or mucosal tissue manifestations and either respiratory compromise or hypotension that requires parental medication intervention	Acute onset of illness with skin and/or mucosal tissue manifestations and either respiratory compromise or hypotension that is life-threatening and requires urgent intervention
